7.1. Discontinuation of Study Intervention

When necessary, a participant may be permanently discontinued from study intervention.

Situations when discontinuation of study intervention may occur

A participant should be permanently discontinued from study intervention if

- the participant becomes pregnant during the study
- a prohibited treatment listed in Section 10.7.3 is initiated during the study, or
- in the opinion of the investigator, the participant should permanently discontinue the study intervention for safety reasons.

If the investigator determines that a systemic hypersensitivity reaction has occurred related to study intervention administration, the participant may be permanently discontinued from the study intervention, and the sponsor's designated medical monitor should be notified. If the investigator is uncertain about whether a systemic hypersensitivity reaction has occurred and whether discontinuation of study intervention is warranted, the investigator should consult the sponsor.

If study intervention is permanently discontinued, the participant will remain in the study and follow procedures for the remaining study visits as shown in the SoA.

7.1.1. Liver Chemistry Stopping Criteria

The study intervention should be interrupted or discontinued if 1 or more of these conditions occur.

Elevation	Exception
ALT or AST >8x ULN	
ALT or AST >5x ULN for more than 2 weeks	
ALT or AST >3x ULN and either TBL >2x ULN or INR >1.5	In participants with Gilbert's syndrome, doubling of direct bilirubin should be used for intervention interruption or discontinuation decisions rather than TBL >2x ULN.
ALT or AST >3x ULN with the appearance of fatigue, nausea, vomiting, right upper quadrant pain or tenderness, fever, rash, and/or eosinophilia (>5%)	
ALP >3x ULN, when the source of increased ALP is the liver	
ALP >2.5x ULN and TBL > 2x ULN	In participants with Gilbert's syndrome, doubling of direct bilirubin should be used for intervention interruption or discontinuation decisions rather than TBL >2x ULN.

ALP >2.5x ULN with the appearance of fatigue, nausea, vomiting, right upper quadrant pain or tenderness, fever, rash, and/or eosinophilia (>5%)	
---	--

Resumption of the study intervention can be considered only in consultation with the Lilly-designated medical monitor and only if the liver test results return to baseline and if a self-limited, non-intervention etiology is identified.

7.1.2. QTc Stopping Criteria

If a clinically significant finding is identified, including, but not limited to changes from baseline in QT interval corrected using Fridericia's formula after enrollment, the investigator or qualified designee will determine if the participant can continue in the study and if any change in participant management is needed. This review of the ECG printed at the time of collection must be documented. Any new clinically relevant finding should be reported as an AE.

7.2. Participant Discontinuation/Withdrawal from the Study

A participant may withdraw from the study:

- at any time at the participant's own request
- at the request of the participant's designee (for example, parents or legal guardian)
- at the discretion of the investigator for safety, behavioral, compliance, or administrative reasons
- if enrollment in any other clinical study involving an investigational product or enrollment in any other type of medical research judged not to be scientifically or medically compatible with this study
- if the participant, for any reason, requires treatment with a therapeutic agent that is prohibited by the protocol and has been demonstrated to be effective for treatment of the study indication. In this case, discontinuation from the study occurs prior to introduction of the new agent.

Discontinuation is expected to be uncommon.

At the time of discontinuing from the study, if possible, the participant will complete procedures for an early discontinuation visit and safety follow-up, if applicable, as shown in the SoA. See SoA for data to be collected at the time of study discontinuation and follow-up and for any further evaluations that need to be completed. The participant will be permanently discontinued from both the study intervention and the study at that time.

If the participant withdraws consent for disclosure of future information, the sponsor may retain and continue to use any data collected before such a withdrawal of consent. If a participant withdraws from the study, the participant may request destruction of any samples taken and not tested, and the investigator must document this in the site study records.

7.3. Lost to Follow up

A participant will be considered lost to follow-up if he or she repeatedly fails to return for scheduled visits and is unable to be contacted by the study site. Site personnel or designee are expected to make diligent attempts to contact participants who fail to return for a scheduled visit or were otherwise unable to be followed up by the site.

8. Study Assessments and Procedures

Study procedures and their timing are summarized in the SoA.

Immediate safety concerns should be discussed with the sponsor immediately upon occurrence or awareness to determine if the participant should continue or discontinue study intervention.

Adherence to the study design requirements, including those specified in the SoA, is essential and required for study conduct.

All screening evaluations must be completed and reviewed to confirm that potential participants meet all eligibility criteria. The investigator will maintain a screening log to record details of all participants screened and to confirm eligibility or record reasons for screening failure, as applicable.

8.1. Efficacy Assessments

8.1.1. Primary Efficacy Assessment

Even though TGs, LDL-C, and non-HDL-C are routinely measured in clinical practices and commonly used as primary endpoints in clinical trials for mixed dyslipidemia, ApoB is considered the strongest predictor of future cardiovascular events.

8.1.2. Secondary Efficacy Assessments

At times specified in the SoA, blood samples will be collected to measure changes in levels of these markers for mixed dyslipidemia

- ANGPTL3
- LDL-C
- HDL-C
- Non-HDL-C, and
- TGs.

8.2. Safety Assessments

Planned time points for all safety assessments are provided in the SoA.

8.2.1. Physical Examinations

Physical examination at screening

The complete physical examination will include assessments of these areas and body systems

- Skin
 - Head
 - Abdomen
 - Extremities
- Ears, eyes, nose, throat
- Lymph nodes
- Thyroid palpation

- Cardiovascular
- Respiratory
- Gastrointestinal, and
- Neurologic.

Height and weight will also be measured and recorded.

The complete physical examination excludes pelvic, rectal, and breast examinations, unless clinically indicated.

Symptom-directed physical assessments after screening

These assessments are performed based on participant status and standard of care.

8.2.2. Vital Signs

Blood pressure and pulse rate will be measured when specified in the SoA and as clinically indicated. Additional vital signs may be measured during study visits if warranted, as determined by the investigator.

Vital signs should be measured after participant has been sitting at least 5 minutes, before obtaining an ECG tracing, and before collection of blood samples for laboratory testing.

8.2.3. Electrocardiograms

Single 12-lead ECG will be obtained as outlined in the SoA using an ECG machine that preferably automatically calculates the heart rate and measures PR, QRS, QT, and QTc intervals.

Electrocardiograms will initially be interpreted by the investigator or qualified designee at the site as soon after the time of ECG collection as possible, and ideally while the participant is still present, to determine whether the participant meets entry criteria and for immediate participant management, should any clinically relevant findings be identified.

The investigator or qualified designee is responsible for determining if any change in participant management is needed and must document their review of the ECG printed at the time of evaluation.

8.2.4. Magnetic Resonance Imaging

Participants will undergo MRI evaluations as outlined in the SoA for the measurement of liver fat content.

Liver fat content will be determined using MRI – Proton Density Fat Fraction. The fat fraction is the proportion of mobile protons in liver tissue attributable to fat and is a noninvasive MRI-based biomarker of liver TG concentration.

MRI images will be transmitted to a central reader for evaluation of the MRI-based endpoints. For participant safety, images should also be over-read locally to assure there are no underlying liver pathologies.

For participants with claustrophobia in MRI machines, investigators may offer, at their discretion, a light sedative.

8.2.5. Clinical Safety Laboratory Tests

See Section 10.2 for the list of clinical laboratory tests to be performed and the SoA for the timing and frequency.

The investigator must review the laboratory results, document this review, and report any clinically relevant changes occurring during the study as an AE.

The laboratory results must be retained with source documents unless a Source Document Agreement or comparable document cites an electronic location that accommodates the expected retention duration.

Clinically significant abnormal laboratory findings are those which are not associated with the underlying disease, unless judged by the investigator to be more severe than expected for the participant's condition.

All laboratory tests with values considered clinically significantly abnormal during participation in the study should be repeated until the values return to normal or baseline or are no longer considered clinically significant by the investigator or medical monitor.

If such values do not return to normal/baseline within a period of time judged reasonable by the investigator, the etiology should be identified and the sponsor notified.

All protocol-required laboratory assessments, as defined in Section 10.2, must be conducted in accordance with the SoA, standard collection requirements, and laboratory manual.

If laboratory values from non-protocol specified laboratory assessments performed at an investigator-designated local laboratory require a change in participant management or are considered clinically significant by the investigator (for example, SAE or AE or dose modification), then report the information as an AE.

8.2.6. Hepatic Monitoring

Close hepatic monitoring

Initiating laboratory and clinical monitoring for abnormal liver laboratory test results

Laboratory tests, including ALT, AST, ALP, TBL, direct bilirubin, GGT, and CK, should be repeated within 48 to 72 hours to confirm the abnormality and to determine if it is increasing or decreasing, if 1 or more of these conditions occur. This table shows when to repeat laboratory tests.

If a participant with baseline results of ...	develops the following elevations:
ALT or AST <1.5x ULN	ALT or AST \geq 3x ULN
ALP <1.5x ULN	ALP \geq 2x ULN
TBL <1.5x ULN	TBL \geq 2x ULN (except for participants with Gilbert's syndrome)
ALT or AST \geq 1.5x ULN	ALT or AST \geq 2x baseline
ALP \geq 1.5x ULN	ALP \geq 2x baseline
TBL \geq 1.5x ULN	TBL \geq 1.5x baseline (except for participants with Gilbert's syndrome)

What to do if the abnormal condition persists or worsens

If the abnormal liver test result persists or worsens, clinical and laboratory monitoring, and evaluation for possible causes of abnormal liver tests should be initiated by the investigator in consultation with the Lilly-designated medical monitor. At a minimum, this evaluation should include physical examination and a thorough medical history, including

- symptoms
- recent illnesses, for example, heart failure, systemic infection, hypotension, or seizures
- recent travel
- history of concomitant medications, including over-the-counter, herbal and dietary supplements, and
- history of alcohol drinking and other substance abuse.

Frequency of monitoring

Initially, monitoring of symptoms and liver tests should be done 1 to 3 times weekly, based on the participant's clinical condition and liver test results.

Subsequently, the frequency of monitoring may be lowered to once every 1 to 2 weeks, if the participant's clinical condition and laboratory results stabilize.

Monitoring of ALT, AST, ALP, and TBL should continue until levels normalize or return to approximate baseline levels.

Comprehensive hepatic evaluation***When to perform a comprehensive evaluation***

A comprehensive evaluation should be performed to search for possible causes of liver injury if 1 or more of the conditions in this table occur.

If a participant with baseline results of...	develops the following elevations:
ALT or AST <1.5x ULN	ALT or AST \geq 3x ULN with hepatic signs/symptoms ^a , or ALT or AST \geq 5x ULN
ALP <1.5x ULN	ALP \geq 3x ULN
TBL <1.5x ULN	TBL \geq 2x ULN (except for participants with Gilbert's syndrome)
ALT or AST \geq 1.5x ULN	ALT or AST \geq 2x baseline with hepatic signs/symptoms ^a , or ALT or AST \geq 3x baseline
ALP \geq 1.5x ULN	ALP \geq 2x baseline
TBL \geq 1.5x ULN	TBL \geq 2x baseline (except for participants with Gilbert's syndrome)

^aHepatic signs/symptoms are severe fatigue, nausea, vomiting, right upper quadrant abdominal pain, fever, rash, and/or eosinophilia >5%.

What a comprehensive evaluation should include

At a minimum, this evaluation should include

- physical examination and a thorough medical history, as outlined above
- tests for
 - PT-INR
 - viral hepatitis A, B, C, or E

- autoimmune hepatitis, and
- an abdominal imaging study, for example, ultrasound or computed tomography scan.

Based on the patient's history and initial results, further testing should be considered in consultation with the Lilly-designated medical monitor, including tests for

- hepatitis D virus
- cytomegalovirus
- Epstein-Barr virus
- acetaminophen levels
- acetaminophen protein adducts
- urine toxicology screen
- Wilson's disease
- blood alcohol levels
- urinary ethyl glucuronide, and
- blood phosphatidylethanol.

Based on the circumstances and the investigator's assessment of the participant's clinical condition, the investigator should consider referring the participant for a hepatologist or gastroenterologist consultation, magnetic resonance cholangiopancreatography, endoscopic retrograde cholangiopancreatography, cardiac echocardiogram, or a liver biopsy.

Additional hepatic data collection (hepatic safety CRF) in study participants who have abnormal liver tests during the study

If a participant develops a hepatic event considered to be an SAE, or discontinues study intervention due to a hepatic event, then collect additional hepatic safety data collection in the hepatic safety CRFs.

This table shows when to collect additional hepatic safety data based on changes in laboratory results.

If a participant with baseline results of...	develops the following elevations...	Then...
Elevated serum ALT		Collect additional hepatic safety data in the hepatic safety CRF.
ALT <1.5x ULN	ALT to $\geq 5x$ ULN on 2 or more consecutive blood tests	
ALT $\geq 1.5x$ ULN	ALT $\geq 3x$ baseline on 2 or more consecutive blood tests	
Elevated TBL		
TBL <1.5x ULN	TBL $\geq 2x$ ULN (except for participants with Gilbert's syndrome)	
TBL $\geq 1.5x$ ULN	TBL $\geq 2x$ baseline	
Elevated ALP		
ALP <1.5x ULN	ALP $\geq 2x$ ULN on 2 or more consecutive blood tests	
ALP $\geq 1.5x$ ULN	ALP to $\geq 2x$ baseline on 2 or more consecutive blood tests	

Note: The interval between the 2 consecutive blood tests should be at least 2 days.

8.2.7. Pregnancy Testing

Pregnancy testing will occur throughout the duration of the study as outlined in the SoA.

8.3. Adverse Events, Serious Adverse Events, and Product Complaints

The definitions of these events can be found in Section 10.3.

- AEs
- SAEs, and
- PCs.

These events will be reported by the participant (or, when appropriate, by a caregiver, surrogate, or the participant's legally authorized representative).

The investigator and any qualified designees are responsible for detecting, documenting, and recording events that meet these definitions and remain responsible for following up events that are serious, considered related to the study intervention or study procedures, or that caused the participant to discontinue the study intervention or the study.

Care will be taken not to introduce bias when detecting events. Open-ended and non-leading verbal questioning of the participant is the preferred method to inquire about event occurrences.

After the initial report, the investigator is required to proactively follow each participant at subsequent visits/contacts. All SAEs will be followed until resolution, stabilization, the event is otherwise explained, or the participant is lost to follow-up (as defined in Section 7.3). For PCs, the investigator is responsible for ensuring that follow-up includes any supplemental investigations as indicated to elucidate the nature and/or causality. Further information on follow-up procedures is provided in Section 10.3.4.

8.3.1. Timing and Mechanism for Collecting Events

This table describes the timing, deadlines, and mechanism for collecting events.

Event	Collection Start	Collection Stop	Timing for Reporting to Sponsor or Designee	Mechanism for Reporting	Back-up Method of Reporting
Adverse Event					
AE	Signing of the informed consent form (ICF)	Participation in study has ended	As soon as possible upon site awareness	AE CRF	N/A
Serious Adverse Event					
SAE and SAE updates – prior to start of study intervention and deemed reasonably possibly related with study procedures	Signing of the ICF	Start of intervention	Within 24 hours of awareness	SAE CRF	SAE paper form
SAE and SAE updates – after start of study intervention	Start of intervention	Participation in study has ended	Within 24 hours of awareness	SAE CRF	SAE paper form
SAE ^a – after participant's study participation has ended and the investigator becomes aware	After participant's study participation has ended	N/A	Promptly	SAE paper form	N/A

Event	Collection Start	Collection Stop	Timing for Reporting to Sponsor or Designee	Mechanism for Reporting	Back-up Method of Reporting
Pregnancy					
Pregnancy in female participants and female partners of male participants	After the start of study intervention	4 days after the last dose of intervention	Within 24 hours (see Section 8.3.2)	Pregnancy paper form	Pregnancy paper form
Product Complaints (PCs)					
PC associated with an SAE or might have led to an SAE	Start of study intervention	End of study intervention	Within 24 hours of awareness	PC form	N/A
PC not associated with an SAE	Start of study intervention	End of study intervention	Within 1 business day of awareness	PC form	N/A
Updated PC information	—	—	As soon as possible upon site awareness	Originally completed PC form with all changes signed and dated by the investigator	N/A
PC (if investigator becomes aware)	Participation in study has ended	N/A	Promptly	PC form	

^aSerious adverse events should not be reported unless the investigator deems them to be possibly related to study treatment or study participation.

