Laboratory Tests and Sample Collections														On dosing days, collect samples before dosing.	
Hematology	X					X			X			X	X	X	
Clinical Chemistry	X	X	X	X	X	X	X	X	X	X	X	X	X	X	
Lipid panel	X	X	X	X	X	X	X	X	X	X	X	X	X	X	Includes non-HDL-C.
Coagulation panel	X	X	X	X	X	X	X	X	X	X	X	X	X	X	
ApoB, ApoA-I, ApoC-III	X	X	X	X	X	X	X	X	X	X	X	X	X	X	
ANGPTL3 and ANGPTL3/8	X	X	X	X	X	X	X	X	X	X	X	X	X	X	
TSH	X														
HbA1c	X	X				X			X			X	X		
Insulin		X				X			X			X	X		
Urinalysis	X					X			X			X	X	X	
UACR	X					X			X			X	X	X	Urinary albumin/creatinine ratio calculation.

Study J3F-MC- EZCB(e)	Screen ing	Double-Blind Treatment and Assessment											Follow- up	Comments	
				X	X	X		X	X		X	X			
Remote Visits			X	X	X		X	X		X	X				V801 on-site for all sites including the US
Visits	1	2	3	4	5	6	7	8	9	10	11	12	ED	801	ED = early discontinuation.
Days from randomization	-45	0	15	30	60	90	120	150	180	210	240	270	—	360	
Visit interval tolerance (days)		—	±3	±3	±3	-5 to +10	±7	±7	±7	±7	±7	±7	—	±7	Visit 1 procedures may be conducted over more than 1 day if all activities are completed within the allowable visit tolerance.
Fasting Visit	X	X	X	X	X	X	X	X	X	X	X	X	X	X	Participants should not eat or drink anything but water for 8 hours before the visit. If a participant arrives not fasted, schedule the laboratory draw for another date.
Serum pregnancy	X														Only for WOCBP and women with a history of tubal ligation. See Section 10.4.
Urine pregnancy (local)		X				X			X			X	X		Collect for WOCBP only. This test must be performed at Visits 2, 6, 9, and end of study with the result available prior to first dose of intervention. Perform additional pregnancy tests if a menstrual period is missed, if there is clinical suspicion of pregnancy, or as required by local law or regulation.
FSH	X														Optional. Perform as needed to confirm postmenopausal status. See Section 10.4.
Hepatitis B virus (HBV)	X														
Hepatitis C virus (HCV)	X														
HIV	X														
Estimated glomerular filtration rate (eGFR)	X	X		X		X			X			X	X	X	Calculated using the Chronic Kidney Disease Epidemiology Collaboration (CKD-EPI) method.

Study J3F-MC- EZCB(e)	Screening	Double-Blind Treatment and Assessment											Follow-up	Comments	
Remote Visits			X	X	X		X	X		X	X				V801 on-site for all sites including the US
Visits	1	2	3	4	5	6	7	8	9	10	11	12	ED	801	ED = early discontinuation.
Days from randomization	-45	0	15	30	60	90	120	150	180	210	240	270	—	360	

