8.3.2. Pregnancy

Collection of pregnancy information

Male participants with partners who become pregnant

The investigator will attempt to collect pregnancy information on any male participant's female partner who becomes pregnant while the male participant is in this study. This applies only to male participants who receive LY3561774.

After learning of a pregnancy in the female partner of a study participant, the investigator will obtain a consent to release information from the pregnant female partner directly, and within 24 hours after obtaining this consent will record pregnancy information on the appropriate form and submit it to the sponsor.

The female partner will also be followed to determine the outcome of the pregnancy. Information on the status of the mother and child will be forwarded to the sponsor. Generally, the follow-up will be no longer than 6 to 8 weeks following the estimated delivery date. Any termination of the pregnancy will be reported regardless of gestational age, fetal status (presence or absence of anomalies) or indication for the procedure.

Female participants who become pregnant

The investigator will collect pregnancy information on any female participant who becomes pregnant while participating in this study. The initial information will be recorded on the appropriate form and submitted to the sponsor within 24 hours of learning of a participant's pregnancy.

The participant will be followed to determine the outcome of the pregnancy. The investigator will collect follow-up information on the participant and the neonate and the information will be forwarded to the sponsor. Generally, follow-up will not be required for longer than 6 to 8 weeks beyond the estimated delivery date. Any termination of pregnancy will be reported, regardless of gestational age, fetal status (presence or absence of anomalies) or indication for the procedure.

While pregnancy itself is not considered to be an AE or SAE, any pregnancy complication or elective termination of a pregnancy for medical reasons will be reported as an AE or SAE.

A spontaneous abortion (occurring at <20 weeks gestational age) or still birth (occurring at ≥20 weeks gestational age) is always considered to be an SAE and will be reported as such.

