Any post-study pregnancy-related SAE considered reasonably related to the study intervention by the investigator will be reported to the sponsor as described in Section 8.3.1. While the investigator is not obligated to actively seek this information in former study participants, he or she may learn of an SAE through spontaneous reporting.

Any female participant who becomes pregnant while participating in the study will be withdrawn from the study. If the participant is discontinued from the study, follow the standard discontinuation process and continue directly to the follow-up phase. The follow-up on the pregnancy outcome should continue independent of intervention or study discontinuation.

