10.1. Appendix 1: Regulatory, Ethical, and Study Oversight Considerations

10.1.1. Regulatory and Ethical Considerations

This study will be conducted in accordance with the protocol and with the following:

- Consensus ethical principles derived from international guidelines including the Declaration of Helsinki and CIOMS International Ethical Guidelines
- Applicable ICH GCP Guidelines
- Applicable laws and regulations

The protocol, protocol amendments, ICF, IB, and other relevant documents (for example, advertisements) must be submitted to an IRB/IEC by the investigator and reviewed and approved by the IRB/IEC before the study is initiated.

Any amendments to the protocol will require IRB/IEC approval before implementation of changes made to the study design, except for changes necessary to eliminate an immediate hazard to study participants.

Protocols and any substantial amendments to the protocol will require health authority approval prior to initiation except for changes necessary to eliminate an immediate hazard to study participants.

The investigator will be responsible for the following:

- Providing written summaries of the status of the study to the IRB/IEC annually or more frequently in accordance with the requirements, policies, and procedures established by the IRB/IEC.
- Notifying the IRB/IEC of SAEs or other significant safety findings as required by IRB/IEC procedures.
- Providing oversight of study conduct for participants under their responsibility and adherence to requirements of 21 Code of Federal Regulations (CFR), ICH guidelines, the IRB/IEC, European regulation 536/2014 for clinical studies (if applicable), and all other applicable local regulations.

Investigator sites are compensated for participation in the study as detailed in the CTA.

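### The Section 8.3.1 table stops pregnancy collection about Day 94, but Section 8.3.2 runs it to the end of participation (Day 270 or 360), so a site following the table may under-report, chiefly partner pregnancies

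*Protocol*

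**What the plan says.** Protocol Section 8.3.1 tabulates when each type of event is collected. The pregnancy row covers female participants and female partners of male participants. It starts after the start of study intervention and stops "4 days after the last dose of intervention". The row refers to Section 8.3.2 only in the cell giving the 24-hour reporting time, not in the cell giving the stop. In the same table, AEs, and SAEs arising after intervention starts, are collected until study participation ends.

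Section 8.3.2 sets a different window. For women in the trial: "The investigator will collect pregnancy information on any female participant who becomes pregnant while participating in this study". For men, the investigator attempts to collect information on a "female partner who becomes pregnant while the male participant is in this study", with the partner's consent, and "This applies only to male participants who receive LY3561774".

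Two further statements in Section 8.3.2 bear on how much is lost: "Any female participant who becomes pregnant while participating in the study will be withdrawn from the study", and "The follow-up on the pregnancy outcome should continue independent of intervention or study discontinuation".

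The Schedule of Activities (Section 1.3) requires urine pregnancy testing of women of childbearing potential well after dosing has finished: "This test must be performed at Visits 2, 6, 9, and end of study".

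**The concern.** The two subsections give different answers to the same question: until when must a site report a pregnancy? One ties the window to the last dose, the other to study participation. There are only two doses, three months apart, and follow-up is long, so the windows differ by months.

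The table is where a site looks up what to collect and when. A site that applies it literally could decide that a pregnancy learned of at, say, Day 180 lies outside the collection period, although Section 8.3.2 says to collect it. The consequence would be incomplete pregnancy data for a new siRNA, with the loss depending on which subsection each site happened to follow. This concerns completeness of safety data. It does not touch the ApoB analysis, its power or its type I error.

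**Working it through.** **Inputs**

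- Second dose: Day 90, window -5 to +10 days, so Day 85 to Day 100 (Sections 1.3 and 4.1).
- Table stop: last dose plus 4 days (Section 8.3.1).
- End of participation: Day 270, or Day 360 for those whose ApoB has not returned to at least 80% of baseline (Sections 1.1 and 1.3).
- Urine tests after the second dose: Visit 9 (Day 180 ± 7) and Visit 12 (Day 270 ± 7) (Section 1.3).
- Randomisation: about 175 participants, 2:1:2:2 for placebo, 100 mg, 400 mg and 800 mg (Section 9.5).

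The plan states no figure for the length of this gap, so there is none to reproduce.

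**Table stop and uncovered period, two-dose participants**

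Stop = second-dose day + 4. Gap = nominal end of participation - stop.

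| Second dose | Table stop | Gap to Day 270 | Share of 270 days | Gap to Day 360 | Share of 360 days |
|---|---|---|---|---|---|
| Day 85 | 85 + 4 = 89 | 270 - 89 = 181 | 67% | 360 - 89 = 271 | 75% |
| Day 90 | 90 + 4 = 94 | 270 - 94 = 176 | 65% | 360 - 94 = 266 | 74% |
| Day 100 | 100 + 4 = 104 | 270 - 104 = 166 | 61% | 360 - 104 = 256 | 71% |

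**Participants given only the Day 0 dose**

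The table stops at 0 + 4 = Day 4. Section 7.1 keeps participants who discontinue intervention in the study, so the gap is 270 - 4 = 266 days, or 360 - 4 = 356 days.

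**Scheduled tests against the table stop**

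- Visit 9 falls between Day 173 and Day 187, which is 173 - 104 = 69 to 187 - 89 = 98 days after the stop.
- Visit 12 falls between Day 263 and Day 277, which is 263 - 104 = 159 to 277 - 89 = 188 days after the stop.

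Under every allowed combination of dates, both tests fall outside the table's window. The protocol therefore mandates tests whose positive results its own table would not collect. The grid marks no urine test at Visit 801, although the comment's reference to the end of study could be read to include that visit.

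**Ceiling on the partner rule**

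Participants randomised to LY3561774: 175 × (1 + 2 + 2)/7 = 125, before restricting to men. This is a loose upper bound on participants, not a count of pregnancies.

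**Which window the rest of the protocol supports**

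- Section 8.2.7 has pregnancy testing running for the whole study.
- Section 10.4.2 requires men with partners of childbearing potential to remain abstinent or use contraception for the study duration and beyond it.
- The AE row, and the SAE row for events after intervention starts, run to the end of participation.
- Section 2.2 reports that the pharmacodynamic effect in Phase 1 lasted to the final collection point at Day 169, far beyond 4 days.

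All of these fit Section 8.3.2 better than the table.

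**The case against.** The strongest reply is that this is one cell at odds with a fuller, dedicated section, and that several safeguards limit the harm.

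- **Female participants.** A pregnant participant must be withdrawn, and outcome follow-up continues regardless. Spontaneous abortion, stillbirth and congenital anomaly are SAEs, which are collected to the end of participation. This stands: the risk for female participants is reduced. The withdrawal rule is not stated consistently, however. Section 7.1 lists pregnancy as a reason to stop intervention and then keeps such participants in the study.
- **Partners.** Section 8.3.2 asks only for an attempt, needs the partner's consent and is limited to men who receive LY3561774. This also stands. Investigators are blinded (Section 6.3), so a site could not apply that limit itself without unblinding. The ceiling of 125 is therefore of little practical use.
- **Contraception.** Men, and women of childbearing potential who are not abstinent, must use contraception. This lowers the expected number of pregnancies but does not settle whether one that occurs is reported.
- **Detection versus reporting.** Scheduled tests find pregnancies, while the table cell governs whether known ones are reported. Changing the cell would detect none among partners. The ranking of partners as most exposed therefore rests mainly on the withdrawal rule, which does not reach them.
- **Intent.** Four days could be a deliberate plasma-washout window. With a mean half-life of 5.5 to 12.9 hours in Phase 1 Part A (Section 2.2), 96 hours is 96/12.9 = 7.4 to 96/5.5 = 17.5 half-lives. The protocol does not give this as the reason. If it were, Section 8.3.2 would need changing instead, and the two sections would still conflict as they stand.

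**Conclusion.** The concern holds. The two collection windows contradict each other in current text, and nothing reconciles them. For a participant dosed on schedule the difference is 176 days to Day 270 (65% of the period after the first dose), or 266 days to Day 360 (74%). Across the dosing window the ranges are 166 to 181 days and 256 to 271 days. For a participant given one dose it is 266 or 356 days.

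These gaps use nominal Days 270 and 360 and describe time left uncovered. They are not estimates of missed pregnancies: the documents give no number of men or of women of childbearing potential, and no expected pregnancy rate. Under-reporting also depends on a site following the table rather than Section 8.3.2. Naming partner pregnancies as the main exposure is an inference from the safeguards that apply only to female participants.

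The point should be corrected because a site following a stated rule would omit data the protocol elsewhere asks for. It has no bearing on efficacy conclusions.

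**What to change.** In the pregnancy row of Section 8.3.1, replace the Collection Stop entry with the end-of-participation stop already used in the AE row, and add that outcome follow-up continues per Section 8.3.2. The added words matter: without them, withdrawing a pregnant participant would appear to close collection of her pregnancy outcome.

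The sponsor should confirm that the participation-based window is the intended one, as the rest of the protocol suggests. If an exposure-based window was meant, Section 8.3.2 should be changed to match and the reason given.

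The edit is one cell and adds no reporting beyond what Section 8.3.2 already asks. The cost is procedural, since "Any amendments to the protocol will require IRB/IEC approval before implementation of changes made to the study design". It is best bundled with the next amendment.
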